A one-sided p-value ≤ 0.05 will be considered significant, based on the assumption that evolocumab will reduce, and not increase, inflammation.

- c. Statistical plan including sample size justification and interim data analysis.

We are providing power calculations for the primary as well as key secondary endpoints (see Tables 1-4).

Primary endpoint:

For calculation of power for the primary endpoint, we anticipate median baseline presentation LDL-C of 110 (90 – 130) mg/dL in our patient population. This number is informed by prior ACS trials (i.e. TIMI-22) as well as local experience with the ACS population at the Johns Hopkins Hospital (with approximately 25%-35% of the population already on baseline statin therapy). We expect this LDL-C value to be reduced by approximately 50% by high intensity statin therapy in the standard treatment arm (i.e. LDL-C of 55 (40- 70) mg/dL at 30 days). We anticipate a further 50% lowering of LDL-C at 30 days after the administration of evolocumab (i.e. LDL-C of 28 (14 – 42) mg/dL. As is shown below (Table 1), using a one-sided p-value of 0.05, the study has nearly 100% power to detect this difference, and will have 80% power to detect an absolute LDL-C reduction of 9.5 mg/dL (17% reduction in LDL-C at 30 days). Additionally, Table 2 presents the expected mean \pm SD baseline and 30-day LDL-C levels and the expected percent LDL-C change in the placebo and evolocumab arms.

Table 1

N in each group	Median (IQR) LDL-C in ACS Population at baseline	Anticipated Percent LDL-C Reduction in the Standard of Care Arm	Estimated Power to Detect a 50% Additional LDL Lowering	Detectable Point Estimate at 80% Power
N = 30	110 (90-130)	50% (40 – 60%)	99+%	-9.5 mg/dL

Table 2: Expected mean \pm SD LDL-C levels at baseline and thirty days and the percent change from baseline to 30 days in the placebo and evolocumab groups.

Groups:		LDL-C, mg/dl		% change from baseline, mean (SD)
		Baseline, mean (SD)	30 day, mean (SD)	
Atorvastatin 80mg	+Placebo	110 (\pm 14)	55 (\pm 11)	-50 (\pm 12)
	+Evolocumab		28 (\pm 10)	-75 (\pm 14)

Secondary Endpoint:

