Previously published clinically relevant, drug-induced TBR changes are reported in the range of 5%-15%. [46] The power calculations for a 10% and 15% TBR difference based on a sample size of 30 patients per study arm are outlined in Table 3 & 4 below. The primary outcome for this calculation of sample is the % difference in TBR between the groups at 30 days in the most diseased segment of aorta or carotid artery. Table 1 uses a 1-sided p-value of 0.05, under the hypothesis that evolocumab will lower inflammation and will not raise it, consistent with the approach used in the Dal-PLAQUE study. For completeness, we replicated the analysis in Table 4 using a 2-sided p-value of 0.05. Calculations are performed using non-parametric statistics accounting for the possibility of non-normally distributed TBR data; calculations using parametric statistics and the following anticipated means and standard deviations yield similar results, as shown in Table 5 below:

Table 3: Power calculations using a 1-sided p-value, i.e. only assumes that PCSK9 inhibition will lower TBR in the most diseased segment (MDS) and will not raise TBR.

		Estimated Power	Detectable
--	--	-----------------	------------

	N in each group	Median (IQR) TBR in ACS Population at 30 days	at 10% & 15% TBR Difference	Point Estimate at 70% & 80% Power
Aorta MDS	N = 30	3.2 (2.7 – 4.0)	66% 93%	-10.6% -12.0%
Carotid MDS	N = 30	2.5 (2.1 – 3.0)	78% 98%	-9.0% -10.2%

Table 4: Power calculations using a standard 2-sided p-value of 0.05

	N in each group	Median (IQR) TBR in ACS Population at 30 days	Estimated Power at 10% & 15% TBR Difference	Detectable Point Estimate at 70% & 80% Power
Aorta MDS	N = 30	3.2 (2.7 – 4.0)	54% 87%	-12.0% -13.6%
Carotid MDS	N = 30	2.5 (2.1 – 3.0)	68% 95%	-10.4% -11.6%

The tables above show fair to good power to demonstrate a difference of 10%, and an excellent power to show a difference of 15% in the primary outcome.

Mean and standard deviations of anticipated TBR in ACS population at 30 days:

- Aorta MDS: 3.3 ± 0.6
- Carotid artery MDS: 2.6 ± 0.4

Table 5: Power calculations using a 1-sided p-value of 0.05 and assuming a normal distribution.

	N in each group	Mean (SD) TBR in ACS Population at 30 days	Estimated Power at 10% & 15% TBR Difference	Detectable Point Estimate at 70% & 80% Power
Aorta MDS	N = 30	3.3 (0.6)	69% 94%	-10.3% -11.8%
Carotid MDS	N = 30	2.6 (0.4)	81% 98%	-8.7% -10.0%

d. Early stopping rules.

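### Power for the PET target-to-background ratio (TBR) rests on SDs about 60% of those implied by the IQRs in the same table rows; with those IQRs it is about 34–44% (10% difference) and 58–75% (15%), not 66–78% and 93–98%

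*Combined protocol and SAP*

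**What the plan says.** Section 7.c (Secondary Endpoint) presents "The power calculations for a 10% and 15% TBR difference based on a sample size of 30 patients per study arm". The quantity powered is "the % difference in TBR between the groups at 30 days in the most diseased segment of aorta or carotid artery". Table 3 is one-sided, in line with the rule in section 7.b that "A one-sided p-value ≤ 0.05 will be considered significant". Table 4 repeats the exercise two-sided.

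Both tables give 30-day TBR as median (IQR): 3.2 (2.7–4.0) for the aorta and 2.5 (2.1–3.0) for the carotid. On the method the text states: "Calculations are performed using non-parametric statistics accounting for the possibility of non-normally distributed TBR data". It adds that parametric calculations give similar answers (Table 5), using these means and SDs for the same population at 30 days: "Aorta MDS: 3.3 ± 0.6" and "Carotid artery MDS: 2.6 ± 0.4".

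The stated powers at 10% and 15% are:

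- Table 3 (one-sided): aorta 66% and 93%; carotid 78% and 98%.
- Table 4 (two-sided): aorta 54% and 87%; carotid 68% and 95%.

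From these the section draws its conclusion: "fair to good power to demonstrate a difference of 10%, and an excellent power to show a difference of 15" per cent.

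**The concern.** Section 7.c gives two descriptions of the spread of one variable, and they disagree. The aortic IQR is 1.3 wide, but an SD of 0.6 goes with an IQR of about 0.81 (0.6 × 1.349). The carotid IQR is 0.9 wide, but an SD of 0.4 goes with about 0.54 (0.4 × 1.349). If the powers come from the smaller spread, Tables 3 and 4 do not follow from the data summary in their own rows. The agreement with Table 5 is then no independent check, because all three tables share the same SDs.

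Section 7.c counts TBR among the key secondary endpoints and cites drug effects of 5–15% as the clinically relevant range. If power at 10–15% is much lower than claimed, a non-significant PET result says little about whether evolocumab reduces vascular inflammation. A reader relying on the power statement could take it as evidence of no effect.

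**Working it through.** **Inputs (section 7.c).** n = 30 per arm; differences of 10% and 15% of the tabulated median; alpha 0.05, one-sided (Table 3) or two-sided (Table 4); quartiles and SDs as listed above.

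**Formula.** Power = Φ(δ / (SD × √(2/30)) − z), with z = 1.645 one-sided and 1.960 two-sided, and √(2/30) = 0.2582.

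**Step 1: reproduce the plan with SDs of 0.6 and 0.4.** Aorta, 10%, one-sided: δ = 0.32; 0.32 / (0.6 × 0.2582) = 2.066; 2.066 − 1.645 = 0.421; power 66.3%. The other cells follow in the same way:

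| Power at 10% / 15% | Stated | SD 0.6 or 0.4 |
|---|---|---|
| Aorta, one-sided | 66 / 93 | 66.3 / 92.7 |
| Carotid, one-sided | 78 / 98 | 78.1 / 97.6 |
| Aorta, two-sided | 54 / 87 | 54.2 / 87.3 |
| Carotid, two-sided | 68 / 95 | 67.7 / 95.3 |

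All eight agree within 0.5 point. The differences detectable with 80% power also agree within 0.1 point: one-sided 12.0% and 10.3% (stated 12.0% and 10.2%), two-sided 13.6% and 11.6% (stated the same). Table 5, which uses the means 3.3 and 2.6, reproduces as 68.6 / 93.9 and 80.9 / 98.3 (stated 69 / 94 and 81 / 98). Solving the stated powers of Tables 3 and 4 for the SD gives 0.60 and 0.39–0.40.

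**Step 2: spread implied by the tabulated IQRs.** For a normal shape, SD = IQR width / 1.349. Aorta: 1.3 / 1.349 = 0.964. Carotid: 0.9 / 1.349 = 0.667. The SDs used are 0.6 / 0.964 = 62% and 0.4 / 0.667 = 60% of these.

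**Step 3: power with the tabulated IQRs.** Aorta, 10%, one-sided, normal: 0.32 / (0.964 × 0.2582) = 1.286; 1.286 − 1.645 = −0.359; power 36.0%. For a lognormal shape the log-SD is ln(Q3/Q1) / 1.349, which is 0.291 (aorta) and 0.264 (carotid), and δ = −ln(1 − difference). The rank-test columns are simulated Mann-Whitney tests (20,000 replicates), which match the rank test planned in section 7.b.

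| Power at 10% / 15% | Stated | Normal formula | Rank test, normal | Rank test, lognormal |
|---|---|---|---|---|
| Aorta, one-sided | 66 / 93 | 36.0 / 61.2 | 34.2 / 57.6 | 38.5 / 66.7 |
| Carotid, one-sided | 78 / 98 | 42.3 / 70.3 | 40.1 / 66.8 | 43.7 / 74.0 |
| Aorta, two-sided | 54 / 87 | 25.0 / 48.8 | 22.8 / 44.9 | 26.5 / 53.8 |
| Carotid, two-sided | 68 / 95 | 30.5 / 58.6 | 27.9 / 53.8 | 31.1 / 61.7 |

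A shifted lognormal matched to all three quartiles gives a one-sided rank-test power of 41.9 / 72.5 (aorta) and 44.1 / 74.6 (carotid).

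**Step 4: detectable difference, 80% power, one-sided.** Normal: (1.645 + 0.842) × SD × 0.2582 / median = 19.3% (aorta) and 17.1% (carotid). Lognormal: 1 − exp(−2.487 × 0.2582 × log-SD) = 17.1% and 15.6%. Allowing for the rank test's efficiency of 0.955 (divide the SD or log-SD by √0.955) gives 19.8% and 17.5% (normal), and 17.4% and 15.9% (lognormal).

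**Step 5: a possible source.** The upper half of each IQR divided by the full-width constant gives 0.8 / 1.349 = 0.59 and 0.5 / 1.349 = 0.37, which round to 0.6 and 0.4. Baseline LDL-C shows a similar pattern: Table 1 gives 110 (90–130) and Table 2 an SD of 14, whereas 20 / 1.349 = 14.8 and 40 / 1.349 = 29.7. This suggests, but does not prove, that half-widths were converted as if they were full widths.

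**The case against.** **Shape.** Converting an IQR to an SD assumes a distribution, and section 7.c allows for non-normal data. Strictly, SDs of 0.6 and 0.4 are attainable with these quartiles: the lower bounds over all shapes are about 0.46 and 0.32. So the two descriptions are not mathematically incompatible. But for any single-peaked distribution with these three quartiles the smallest SD is about 0.68 (aorta) and 0.46 (carotid), above the values used. A tail-free uniform shape gives a one-sided rank-test power of 46% / 74% (aorta) and 54% / 82% (carotid), and the most favourable quartile-matched shapes tried reach at most about 59% / 88%. The exact replacement figures therefore depend on shape, but every shape tried falls short of the stated powers.

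**Baseline adjustment.** Section 7.b also plans an ANCOVA of percent change in TBR with baseline TBR as covariate, which could be more powerful. To bring the IQR-based SDs down to 0.6 and 0.4, the baseline correlation would have to be √(1 − 0.62²) ≈ 0.78 (aorta) and √(1 − 0.60²) ≈ 0.80 (carotid). The documents give no correlation. If it were 0.5–0.7 (an assumption), power would be about 43–69% at 10% and 71–95% at 15%. This limits the finding to the tabulated comparison, but it does not rescue the tables: they concern the unadjusted 30-day difference, and 0.6 and 0.4 are labelled as SDs of 30-day TBR.

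**Importance.** TBR is a secondary endpoint in what section 3 calls a pilot study, and the LDL-C power does not depend on these inputs. That is so. If the IQRs are the misprint, the powers stand. Nor does the plan say that a null TBR result would be read as no effect; that risk is a judgement.

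**Conclusion.** The concern holds. Tables 3 and 4 were calculated with SDs of 0.6 and 0.4, not with the spread tabulated in their own rows. Taking the tabulated IQRs at face value under normal, lognormal or quartile-matched skewed shapes, one-sided power is about 34–44% at 10% and 58–75% at 15%, against 66–78% and 93–98% stated. Two-sided power is about 23–31% and 45–62% by the simulated normal and lognormal rank tests, against 54–68% and 87–95%. The one-sided difference detectable with 80% power is about 17–20% (aorta) and 16–18% (carotid), above the 5–15% range that the plan itself cites.

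Under these shapes the unadjusted comparison would miss a true 10% effect more often than not, and a 15% effect in about a quarter to two fifths of trials. The result assumes 30 evaluable patients per arm and a single-peaked distribution. The documents cannot settle whether the IQRs or the SDs are wrong, but as written the power statement is unsupported.

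**What to change.** Go back to the source of the TBR data, decide which spread is right, and use it throughout Tables 3–5.

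- **If the IQRs are right:** recalculate Tables 3–5 and name the distribution and the test used. Expect one-sided powers of about 34–44% (10%) and 58–75% (15%) and 80%-power detectable differences of about 16–20%. Remove the claim of excellent power, and state that a non-significant TBR result does not exclude an effect of 10–15%.
- **If the SDs are right:** correct the quartiles in Tables 3 and 4. A normal shape around the stated means gives about 2.9–3.7 for the aorta (3.3 ± 0.6745 × 0.6) and 2.3–2.9 for the carotid (2.6 ± 0.6745 × 0.4). The stated powers then stand.

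If the sponsor wishes to rely on the ANCOVA instead, its power should be shown separately, with the assumed baseline correlation and its source. Because of the similar pattern in Tables 1 and 2, the LDL-C SDs deserve the same check.

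The cost is recalculated tables and one or two sentences. No patients, visits or analyses are added, although in the first case the stated power becomes less favourable.
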